### Objective III A-B: Methodology

#### Determination of appetite and endocrine mediators of appetite

Assessment of appetite and endocrine mediators of appetite will be completed after 1 week of diet acclimation (day 7, baseline), on day 43 (post-energy deficit), and upon return to initial body mass (EOS+1). Participants will receive a fixed-portion breakfast meal (0 min) and an ad libitum lunch meal (180 min). Subjectively rated appetite and blood samples will be collected before and periodically following each meal (Table 3 and Table 4).

**Table 3. Baseline (day 7) and recovery (EOS+1) appetite experiment timeline.**

Time (min)	-15	0	30	60	120	180	185	Post-meal
Meal		x					x	
VAS	x		x	x	x	x		x
Bloods	x		x	x	x	x		

**Table 4. Post-energy deficit appetite experiments (day 43).**

Time (min)	-15	0	30	60	120	180	185	215	245	305	365
Meal		x					x				
VAS	x		x	x	x	x		x	x	x	x
Bloods	x		x	x	x	x		x	x	x	x

VAS, visual analog scale.

A fixed-portion test meal will be served as a breakfast meal on the morning of study days 7, 43 and at EOS+1. This meal will have mixed macronutrient content and be prepared according to a standard procedure. For each participant the energy content of the meal will be equivalent to 20% of the TDEE prescribed for that individual on study days 0-14. Water in the amount of 240 g will be provided during the meal. Participants will be instructed to consume all of the water before completing the meal and will not be permitted additional water during the meal.

A second meal, the lunch meal, will be consumed *ad libitum* 180 min following provision of the breakfast meal. The lunch meal will have a mixed macronutrient content, consist of a single item (e.g., lasagna), and be prepared according to a standard procedure by research staff. A portion calorically equivalent to at least 75% of the TDEE prescribed for that individual on study days 0-14 will be served to ensure that food intake is not limited by the amount served. Participants will be instructed to eat until comfortably full, and be permitted to eat as much or as little as desired. There will be no restrictions on meal duration. The amount of uneaten food will be weighed and the energy content of the portion consumed calculated. Water in the amount of 240 g will be provided. Participants will be instructed to consume all of the water before completing the meal and will not be permitted additional water during the meal. (Diets will be adjusted on day 7 to account for the appetite assessment)

In the intervals between meals participants will be required to drink 360 mL water, and will not be permitted access to any additional food or beverage.

At each blood draw, self-reported fullness, hunger, prospective consumption, and desire to eat will be measured using 100-mm visual analog scales (**Appendix K**). The visual analog scales will be administered by paper and pencil or may be administered on a computer.

Biomarkers of appetite regulation.

An indwelling intravenous catheter into the antecubital vein or forearm of the participant's arm will be placed 30 min prior to the breakfast meal. A fasted blood sample will be taken 15 min before beginning the meal. Blood will be sampled according to the timelines in **Tables 3 and 4**. At each time point 14.5 mL blood will be collected for a total of 275.5 mL over the full study to measure endocrine mediators of appetite. If at any point during the testing period the catheter becomes clogged or is no longer patent it will be removed and replaced. Serum will be analyzed for leptin and insulin (measured at -15 min only), serum for glucose, and plasma for acyl ghrelin and des-acyl ghrelin at PBRC using commercially available assays. Additional samples will be collected at each timepoint and archived for future tests. All samples will be collected using appropriate preservatives to minimize degradation. Blood measure collection time points are shown in **Appendix E**.

Determination of gut microbiome composition and activity, and intestinal permeability  
A single fecal sample will be collected at 4 time points (end of run-in diet [days 11-14], mid-point [days 25-28] and end of intervention [days 39-42], and upon return to initial body weight [EOS-EOS+3]) during the study to assess gut microbiota composition and function. At each time point participants will be given a ≤72-h window to collect a usable sample. A usable sample is defined as being > 25g wet weight, and having been delivered to study staff within 12-h of defecation while being kept cold but not frozen from the time of collection to delivery. If a participant does not provide a usable sample within the timeframe noted above, the collection period will be extended until a usable sample is produced. To collect fecal samples, all participants will be given pre-labeled containers with covers and a plastic device to "hold" the container in the toilet. Participants will defecate into the collection container which will then be given to study staff. During free-living phases of the study participants will be given plastic sealable bags, a cooler and ice packs to store and transport the samples from home (**Appendix L**).

Samples will be processed as soon as possible and within 12-h of defecation. Aliquots for 16s rRNA gene sequencing, transcriptomics, metabolomics, short-chain fatty acids (SCFA) analysis and archiving will be frozen at -80°C. DNA and RNA will be extracted from samples using commercially available kits. Microbiota composition will be assessed by sequencing amplicons targeting the V4 region of the bacterial 16S rRNA gene using appropriate primers and unique barcodes for each sample. Transcriptomics will be completed using RNA-seq. Sequencing will be completed on the Illumina MiSeq or a similar platform, and completed at the Broad Institute (Cambridge, MA) or by a similar entity on a fee-for-service basis. As gut microbiota composition analysis is a rapidly evolving field, the selection of primers, the 16S rRNA

gene variable region to sequence, and the sequencing platform may be modified to be consistent with the literature and technology available at the time of analysis. Quality control of reads and taxonomic assignment (phyla to operational taxonomic unit-level) will be completed using established software and databases. Metabolomics will be completed by Metabolon (Durham, North Carolina) or by a similar entity on a fee-for-service basis. SCFA will be measured as markers of bacterial fermentation at the US Army Natick Soldier Research Development and Engineering Center (NSRDEC) or elsewhere on a fee-for-service basis using gas chromatography and a flame-ionization detector  or an equivalent method.

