**Phase 1: Diet Acclimation (free-living). Day 0–Day 14**

- During the diet acclimation phase, participants will return to Pennington Biomedical once a day to eat and receive additional meals for the day. Participants will be weighed daily and caloric adjustments made if needed. Participants will be asked to record their activity daily throughout the phase. Additionally, 2 accelerometers (wrist- and waist-worn) will be applied at Day 0 and worn through day 14.
- Blood draws will occur on days 0, 7, and 14.
- Cognitive training will be performed on days 0, 2, 4, 6, 8, and 10 for approximately 1.5-2 hours each day. Cognitive testing will be performed on days 5 and 13 over a 2-hour period each day. The timing of training sessions is not critical.
- A DXA will be done on days 0 and 11.
- A 1-hour fMRI will be done approximately on days 5, 9, and 12.
- A food intake test with VAS and gut hormone assessments will be done on day 7.
- Participants will consume 150 mL/d  $^2\text{H}_2\text{O}$  (i.e., heavy water) from day 0 to 7 and 100 mL/d  $^2\text{H}_2\text{O}$  from day 8 to 14.
- Participants will be asked to provide a saliva sample on days 3, 7, and 11 to assess body water enrichment.
- Participants will ingest D3-creatine (D3Cr) (60 mg capsule) on day 11 for estimates of muscle mass at the end of phase 1 (urine collections on days 11, 13, 14).
- On day 11, participants will stay in the metabolic chamber and have urine nitrogen and urine creatinine collected for 24 hours.
- Participants will consume 2 g sucralose dissolved in 180 mL water on the morning of study day 11. A 24-hour urine sample collected with the nitrogen and creatinine testing will be used to analyze the sugar substitute ingestion.
- Participants will be asked to provide a stool sample on day 11 (+72 hours) for gut microbiome analysis.
- Information regarding adverse events will be collected on days 0, 7, and 14.
- A biodex familiarization test will be performed on day 0 and the actual biodex test will be performed on day 13.
- A VO2max treadmill test will be performed on day 0. The test will be used to prescribe exercise intensities.
- Eating Inventories (TFEQ, FCI, FCI trait) will be completed on day 14.
- A bike familiarization ride will be performed within the first week of Phase I. The familiarization ride will be used to establish appropriate settings and exercise workloads for the experimental testing procedures.

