#### **Phase 3: Ab Libitum Feeding (free-living). Day 43–Return to Body Mass**

- For days 43 (participants will be released after completing the final test on day 43) to EOS, participants will return to PBRC at least weekly to weigh-in.
- While participants will report to PBRC approximately once a week to weigh-in, each participant will be provided a scale to take home for daily weight measurements during this time frame. All measures will be semi-nude (t-shirt, shorts, socks) and performed after an overnight fast. Prior to distribution of the scales, they will be verified via PBRC's scale calibration verification SOP with a 50 lb. standard weight. At each weekly check, the participant will be asked to return the scale for reverification to ensure accurate weight measurements.
- Participants will complete a 3-day food record (2 weekdays, 1 weekend day) one week into phase 3 (days 50 to 56).
- Accelerometers (wrist and waist worn) will be worn on days 43 through EOS.
- A food intake test with VAS and gut hormones will be done on day 43.
- Blood draws will occur on day 56.
- Cognitive testing will be performed on day 54
- A DXA will be done on day 53.
- A 1 hour fMRI will be done on days 55, 56, and 57.
- Exercise testing for muscular strength (biodex) will be performed on day 55.
- On day 53, participants will stay in the metabolic chamber and have urine nitrogen and urine creatinine collected for 24 hours.
- Participants will consume D3-creatine (D3Cr) (60 mg capsule) on day 53 for estimates of muscle mass (urine collected on days 53, 55, 56).
- Time commitment during phase 3 will be about 2-3 hours per day on days 54-57. On day 43, the time commitment will be about 4 hours. On day 53 (whole-room calorimetry day), participants will be at the facility for 24 hours. On the once a week weigh-in, participants will be at the facility for approximately 30 minutes.

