#### Determination of aerobic capacity

Aerobic capacity (i.e., peak oxygen uptake, VO2peak) will be measured using an indirect open circuit respiratory system on a treadmill (day 0) during phase 1. Aerobic capacity will be used as a reference point to determine the appropriate exercise workloads necessary to meet the energy requirements for phase 2. In brief, participants will be clothed in appropriate athletic attire and perform this assessment at standard ambient indoor temperature (20-22°C) and humidity conditions (30-80%). Participants will be instructed to refrain from the consumption of food and caffeine for a minimum of 3 hours, following an overnight fast before testing, or following a light snack. Following instruction, participants will be given adequate time to become familiar with the testing procedures and allowed a 5-min self-paced warm-up on the treadmill. At the initiation of testing, the participant will put on a nose clip and a mouthpiece connected to a two way respiratory valve, which is attached to a head piece to hold it in place. Prior to beginning the running protocol, participants will walk for 5 minutes at predetermined comfortable speed and a 0% grade. The participants will then run for 4 minutes at a pace predetermined as comfortable at a 0% grade. At 4-min, the grade will be increased to 4%, followed by an additional 2% every two min thereafter until volitional exhaustion. Heart rate and ratings of perceived exertion (RPE) will be recorded during each stage. Although the testing endpoint will be volitional exhaustion, the test will be stopped immediately if the subject reports angina-like symptoms, exertional syncope, shows signs of poor perfusion (i.e., light-headedness, confusion, ataxia, pallor, cyanosis, nausea, or cold and clammy skin), or if there is a failure of testing equipment.

Testosterone and placebo administration

Participants will receive either 200 mg testosterone enanthate or placebo (sesame oil) by intramuscular injection at the conclusion of all phase 1 testing (morning of day 15) and then weekly on days 21, 28, and 35. Doses and syringes will be prepared by the PBRC clinical research pharmacy and injected by PBRC medical staff. Based on previous dose-response studies, 200 mg of testosterone enanthate was chosen as an effective dose to maintain testosterone within normal physiological ranges while minimizing risk of secondary health effects.

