#### **To collect the stool specimen:**

1. Remove the contents of the collection kit from the drawstring bag.
2. Lift the toilet seat.
3. Place the plastic collection container over the toilet bowl.
4. Lower the toilet seat.
5. Collect the stool in the plastic collection container.
  - Do not contaminate the stool with urine, toilet water, or toilet paper.
  - Do not pass the specimen directly into the transport tube.
6. Use the wooden tongue depressor provided to transfer approximately 5ml of stool to the 30ml graduated stool sample tube provided.
7. Secure the screw cap on the 30ml graduated stool sample tube taking care not to cross thread the cap.
8. Document the collection date and collection time on the label directly on the 30ml graduated stool sample tube.
9. Seal the stool sample tube in the zip-close specimen transport bag containing a small absorbent sheet.
10. Excess stool in the plastic collection container should be discarded in the toilet.
11. Place the used collection container and the wooden tongue depressor in the drawstring bag, tie shut, and dispose in the trash.
12. Wash your hands thoroughly after collecting the specimen.

If you are unable to provide a stool sample while you are at PBRC, you will be instructed to collect a sample at home within 72 hours of the study visit. In order to maintain the quality of the stool sample, **it must remain chilled from the time of collection until it is received at Pennington Biomedical, and it must be delivered to PBRC within 12 hours of collection.** If the time between collection and processing exceeds 12 hours, the sample cannot be used for analysis, and you will be asked to collect another sample.

Notify your study coordinator, [name] at [contact] if you have any questions or concerns.

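### The open-ended stool-collection rule can place a baseline sample inside the energy deficit and an end-of-intervention sample after refeeding, and it conflicts with the 72-hour limit in Appendix E

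*Combined protocol and SAP*

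**What the plan says.** Under Objective III A-B: Methodology, the subsection on gut microbiome composition and intestinal permeability asks for one stool at each of four time points. The first three are "end of run-in diet [days 11-14], mid-point [days 25-28] and end of intervention [days 39-42"; the fourth is EOS to EOS+3. It adds: "At each time point participants will be given a ≤72-h window to collect a usable sample". If that fails, "the collection period will be extended until a usable sample is produced". No outer limit follows.

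The Study Timeline gives the same nominal days. For phase 1: "Participants will be asked to provide a stool sample on day 11 (+72 hours) for gut microbiome analysis". The phase 2 and EOS bullets carry the same 72-hour allowance. The Appendix E footnote on fecal samples also limits collection to the indicated day or the next 72 hours, and mentions no extension.

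The neighbouring events are these:
- Randomization is on day 14, and phase 2 (the 55% deficit) runs from day 15 to day 42.
- Testosterone or placebo is given "by intramuscular injection at the conclusion of all phase 1 testing (morning of day 15) and then weekly on days 21, 28, and 35".
- Phase 3 begins on day 43, and "A food intake test with VAS and gut hormones will be done on day 43". That test is a fixed breakfast followed by an ad libitum lunch.

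On usability, the methods state: "A usable sample is defined as being > 25g wet weight". The sample must also reach staff cold within 12 hours. The fecal collection instructions tell the participant to "transfer approximately 5ml of stool to the 30ml graduated stool sample tube provided" and to discard the remainder.

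**The concern.** Objective III-B asks how stool outcomes change across the deficit, with and without testosterone. The first and third samples define that change, and each window runs to the last day of its phase. If staff follow the methods section and keep the window open, the replacement sample can come from the next condition.

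The protocol hypothesizes that the deficit lowers fecal short-chain fatty acids and bacterial diversity, and that regaining body mass reverses this. On that reasoning, a baseline taken in deficit already contains part of the effect, and an end sample taken after refeeding has lost part of it. Both errors shrink the estimated change. A late baseline is also post-randomization and, once the first injection has been given, can carry a treatment effect.

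Only one stool is collected per time point, so a misplaced sample has no correctly timed companion. The statistics subsection on gut microbiota and metabolomics models study day, group and their interaction. It does not say how a late sample is dated, excluded or examined in a sensitivity analysis.

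**Working it through.** **Inputs.** Nominal stool days 11, 25 and 39, and the window of at most 72 hours (3 days), come from the gut microbiome methods. The deficit start (day 15) and end (day 42) are in the Phase 2 heading. The first injection on the morning of day 15 is under Testosterone and placebo administration. Refeeding from day 43 is in the Phase 3 heading.

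**Step 1: reproduce the stated windows.** Close = nominal day + 3.
- 11 + 3 = 14
- 25 + 3 = 28
- 39 + 3 = 42

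All three match the plan.

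**Step 2: compare each close with the next change of condition.**

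| Window | Closes | Next event | Calendar gap |
|---|---|---|---|
| Baseline | day 14 | deficit and first injection, day 15 | 15 − 14 = 1 |
| Mid-point | day 28 | next stool window, day 39, still in deficit | 39 − 28 = 11 |
| End of intervention | day 42 | test breakfast and refeeding, day 43 | 43 − 42 = 1 |
| EOS | EOS+3 | none; the man is already in free-living recovery | not applicable |

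A calendar gap of 1 is between a few overnight hours and about 24 hours. It is overnight only if the window runs to the end of day 14 or 42. It is about 24 hours if the 72-hour clock starts near 0800 on day 11 or 39, the chamber entry time given in the energy expenditure section, because the clock then stops near 0800 on day 14 or 42.

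**Step 3: place a late sample.** A sample L days after the close falls on day 14 + L (deficit day L) or day 42 + L (refeeding day L).
- L = 1: day 15 or day 43. It is still valid only if passed before the first phase 2 meal and injection, or before the test breakfast.
- L = 2: day 16 or day 44, in the wrong condition.
- L = 7: day 21 or day 49, a full week into the wrong condition.

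**Step 4: possible size, by assumption only.** Let q be the share of men late past the boundary at one time point, and r the share of the deficit change already present (late baseline) or already reversed (late end point). The mean change retained is 1 − qr if one end is affected, and 1 − 2qr if both ends are affected equally. The documents give neither q nor r. Taking q = 5-20% and r = 0.25-1.0:
- One end: from 1 − 0.05 × 0.25 = 0.988 down to 1 − 0.20 × 1.0 = 0.80.
- Both ends: from 1 − 2 × 0.05 × 0.25 = 0.975 down to 1 − 2 × 0.20 × 1.0 = 0.60.

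With the planned 25 completers per arm, q = 5-20% is 25 × 0.05 = 1.25 to 25 × 0.20 = 5 men per arm per time point. The value r = 1 is an extreme, since it means the whole change occurs or reverses before the late sample is passed.

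**Step 5: what could trigger extensions.** If the weight rule applies to the tube that is handed in, and density is assumed near 1 g/mL, a sample collected as instructed weighs about 5 mL × 1 g/mL = 5 g, against a threshold above 25 g. It would fail although the man followed his instructions. If the rule applies to the whole stool, there is no failure. The methods have the collection container handed to staff, while the instruction sheet has the excess discarded, so the text does not settle which reading applies.

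**The case against.** The strongest reply is that the open-ended sentence is not the only rule. The Appendix E footnote and the timeline bullets stop at 72 hours. The note closing the Study Timeline permits only schedule alterations that do not affect outcomes, which argues against collecting across a phase boundary. This stands in part: a reader might infer that the protocol settles on unlimited extension, and it does not. It contains two incompatible rules. The timeline note is discretionary and sets no stool limit, and nothing holds back phase 2 or release until a stool is obtained, so it does not resolve the conflict.

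Second, lateness may be rare. Men attend daily in phase 1, are on site for 24 hours on days 11 and 14, and live on the ward on days 39-42. Gastrointestinal disease and regular laxative use are exclusions. This also stands: no late rate can be derived, and nothing in the documents shows that late samples would come mainly from men with infrequent stools.

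Third, both arms undergo the same deficit and refeeding, so a late sample first distorts the change over time. That is fair. The documents give no basis for saying how far the testosterone contrast would move.

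Fourth, stool outcomes are not the stated primary endpoint, which is total body mass. That limits the importance of the point but does not remove it.

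**Conclusion.** The point holds as a conflict between two collection rules, one of which can place a baseline or end-of-intervention stool in the wrong condition. The timing follows directly from the protocol's own days. The size rests on assumed late rates and assumed speeds of change; the range of 0.60 to 0.988 of the change retained illustrates this and is not an estimate. The direction, toward a smaller change, rests on the protocol's hypothesis that the deficit effect is real and reverses with regain.

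Three stronger readings are tempting and are not supported:
- That every extension contaminates the sample. Up to about a day remains in which a late stool is still in the right phase.
- That late samples will be analysed under the earlier label. The plan is silent on this and does not say whether study day in the model is nominal or actual.
- That a day 43 sample follows a lunch of 75% of daily expenditure. That figure is the minimum portion served; the amount eaten is up to the man.

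The point is worth fixing before collection because the change is small and a mistimed sample could otherwise pass unnoticed.

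**What to change.** 1. In the gut microbiome methods, replace the open extension with a stop. The baseline stool must be passed before the first phase 2 meal and injection on day 15, and the end-of-intervention stool before the day 43 test breakfast. Align the Phase 1 and Phase 2 timeline bullets and the Appendix E footnote with this.
2. Record the actual date and time of every stool. Archive any stool passed after the boundary and treat it as missing for that time point. State in the statistics subsection whether study day is nominal or actual.
3. Reconcile the weight threshold with the participant instruction sheet, so that a sample collected as instructed is not rejected and does not cause an avoidable extension.
4. Optionally, open the two windows earlier to recover time. A baseline opening should not directly follow the day 7 ad libitum test lunch. Earlier stools would also lie further from the permeability tests on days 11 and 39.

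The cost is a few sentences and a few more missing stool samples. No samples or visits are added. The planned mixed models can use the remaining time points for men with one missing stool, provided that missingness is at random given the observed data.
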